8.4. Assessment of muscle perfusion and energetics

If available equipment and personnel are available at the time of enrollment, MRI studies will be performed at rest and immediately after a standardized plantar flexion exercise test using a 3T or a 7T scanner equipped with a 15-channel transmit/receive radiofrequency coil and an MR compatible pneumatically controlled foot pedal. Phase contrast MRI using a fast 1D projection technique¹²⁵ will be used to image blood flow with high temporal resolution (Figure 5a-c).

The primary measure of recovery kinetics will be measured with creatine chemical exchange saturation transfer (CrCEST), except for subjects enrolled at the Northwestern site. Sample CrCEST recovery images of the calf are shown in figure 5d. The first 2 acquisitions are preexercise (red box), with the remainder representing sequential acquisition immediately after cessation of exercise. Recovery kinetics of creatine levels will be quantified. Phosphorus spectroscopy is limited by the lack of anatomic information, being able only to assess PCr levels in a large voxel of tissue. In contrast, the chemical exchange saturation transfer (CEST) technique, a novel sensitivity enhancement method developed by our group,^{75, 126-128} can detect metabolite content based on exchangerelated properties at either 7T^{127, 128} or 3T,¹²⁶ utilizing hydrogen signal (thus not depending on the much weaker phosphorus signal). Creatinine exhibits a concentration dependent CEST effect between its amine (-NH₂) and bulk water protons (CrCEST)⁷⁵ which allows for the monitoring of Cr concentration changes with high spatial and temporal resolution. In contrast to phosphorus spectroscopy, this technique allows for spatial mapping (creation of an highresolution anatomic image) of PCr levels (figure 3D). This cannot be accomplished with phosphorus spectroscopy. This novel technique can be used to assess PCr recovery kinetics following exercise, allowing for accurate selection of muscle tissue (rather than fat or bone). More importantly, the serial anatomically mapped PCr information can be used to assess muscle fat using a 3-point Dixon separation technique and hydrogen spectroscopy. We will exclude fat from CrCEST computations.

8.5. Doppler Echocardiography

This procedure is similar to clinical cardiac echocardiograms. An ultrasound probe will be placed on the surface of the skin to obtain images of the heart. This takes approximately 60 minutes. This will occur at all three visits.

Measurement of LV filling and myocardial strain: Given that inorganic nitrate may also induce venodilation and myocardial effects, we will also assess the effects of potassium nitrate on (1) Early mitral annular early diastolic tissue velocity; (2) The ratio of early diastolic mitral inflow velocity to mitral annular tissue velocity (a surrogate of LV filling pressures); (3) Peak early diastolic intraventricular pressure gradient, a marker of ventricular relaxation, assessed with color M-mode interrogations of mitral inflow.^{129, 130} We note that the latter is not simply based on the inflow propagation velocity, but rather on solving Euler momentum equation.¹²⁹ This method is able to accurately assess LV relaxation.¹²⁹ Systolic function will be assessed via systolic myocardial strain (using speckle tracking echocardiography), which we have successfully applied in previous studies.^{92, 95, 131}

8.6. Measurement of late systolic load and arterial wave reflections:

We will use a high-fidelity Millar applanation tonometer⁸⁰ to record carotid pressure waveforms, which will be calibrated using brachial artery pressures. Central arterial tonometric recordings and Doppler flow velocity files will be processed off-line using custom-designed software written in Matlab (The Mathworks, Natick, MA) as previously described.^{92, 132} We have successfully implemented this method in multiple previous studies^{79, 83, 92, 93, 133} and have published a tutorial detailing our analysis methods.^{78, 79} After signal-averaging of pressure and flow, time alignment of carotid pressure and LV outflow curves will be performed to maximize concordance of the rapid systolic upstroke of pressure and flow, concordance of the dicrotic notch and cessation of flow, zero value of the phase angle of higher-frequency harmonics (7th to 10th) of input impedance, and linearity of the early systolic pressure-flow relationship.¹³² After computation of aortic input impedance, proximal aortic characteristic impedance (Zc) will be computed in the frequency domain as previously described.¹³² Pressure and flow harmonics were separated into forward and backward components using standard wave separation analysis.^{78, 79, 132, 134} The sum of forward and backward pressure harmonics yields the forward and backward waves, respectively. We will

assess the reflection coefficient in the first 3 harmonics. As reflection coefficient is derived from the ratio of two sine waves, it is a complex number with an amplitude and phase-angle, which can correspond to different degrees of destructive or constructive interference between forward and backward waves. Therefore, the net-effect of reflections will be expressed as the real part of Γ , which becomes increasingly positive as pressure from wave reflections increases (constructive interference), and negative when destructive interference leads to a net decrease in pressure by wave reflections at a given harmonic.¹³⁵ Since all harmonics of wave reflection contribute variably to systolic LV load, our primary measure of late systolic load will be the net pressure related to wave reflections during ejection in the time domain, which better represents the impact of reflections on LV afterload. We will first compute the product of flow and aortic Zc (QZc product), which represents the pressure resulting from the interaction of blood flow with aortic root Zc.^{79, 80} The relation between QZc and measured pressure reveals the direct effect of wave reflections on the arterial system.¹³⁶ We will therefore quantify the additional ejection-phase pressure load from wave reflections arising distal to the root (i.e., reflection-related pressure time integral during ejection, as the difference between measured pressure and the QZc product). Carotid-femoral pulse wave velocity (PWV), an index of large artery stiffness,^{137, 138} will also be measured^{80, 139} using a Sphygmocor device (Atcor Medical).¹³⁷ We will also measure carotid-radial PWV using the Sphygmocor device. PWV is not a formal endpoint of this trial, since our pilot trial did not demonstrate an effect of nitrate-rich beetroot juice on this endpoint (unpublished data). However, it may aid in interpreting changes in pulsatile hemodynamics in the trial. Similarly, when available, arterial tonometry may be performed during and immediately after exercise for exploratory purposes.

8.7. Blood nitrate/nitrite level measurements:

We will document an intervention-related change in blood nitrate and nitrite. Nitrate and nitrite levels will be sampled before and approximately 2 hours after the last oral dose on the morning of the exercise test, after the patient has been on each intervention for approximately 6 weeks. Measurements will be performed at [name] lab at the University of Pennsylvania. Venous blood samples will be drawn into lithium-heparin tubes (which have very low levels of nitrate/nitrite) and centrifuged at 4,000 rpm for 10 min within 3 min of collection and frozen at - 80°C for later analysis. Blood will also be obtained at peak exercise. After thawing at room temperature, blood samples will be deproteinized using cold ethanol precipitation as previously described.¹¹⁸ The nitrate and nitrite content of deproteinized blood will be determined using a modified detection chemiluminescence technique using a lonics/Sievers nitric oxide analyzer (NOA 280), as first described by [name] lab¹⁴⁰ and later adapted by Allen et al for human blood.¹⁴¹

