Effects on blood pressure: Regarding the blood pressure reduction, as described above, many studies have demonstrated a reduction in blood pressure in both hypertensive and normal subjects following nitrate supplementation. This was summarized in a recent meta-analysis, demonstrating an approximate 4 mm Hg reduction in systolic blood pressure and 1 mm Hg reduction in diastolic blood pressure.⁵¹ Importantly, in our study of a single dose of inorganic nitrate in this specific population (HFpEF), we did not observe any change in blood pressure following nitrate ingestion. This suggests that subjects with HFpEF may have a different response to nitrate than other populations and thus hypotension may be a less pronounced side effect. Importantly, the lack of a blood pressure response to nitrate has been shown in both elderly ¹⁷⁶ and diabetic individuals,¹⁷⁷ further suggesting that there may be important differences in nitrate effect by subgroups. In our pharmacokinetics study, we found a mild (~12 mm Hg) asymptomatic reduction in blood pressure recorded at the time of our study visits during 2-week drug administration, which occurred in the absence of any hypotensive symptoms.¹⁷⁸ We did not find a reduction in ambulatory blood pressure. Therefore, although we don't anticipate major changes in BP or significant hypotension with this dose, we will implement exclusion criteria and safety

blood pressure checks throughout the conduct of the study to ensure subject safety (see next section).

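### Section 8.6: the primary measure of late systolic load, as written, includes diastolic pressure × ejection time, which is not wave reflection; the pressure reference should be stated

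*Combined protocol and SAP*

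**What the plan says.** Section 8.6 names the lead quantity for late systolic load: "our primary measure of late systolic load will be the net pressure related to wave reflections during ejection in the time domain".

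The computation has two steps. The first is "We will first compute the product of flow and aortic Zc (QZc product"), described as the pressure that arises when flow meets the characteristic impedance of the aortic root. The second is the "reflection-related pressure time integral during ejection, as the difference between measured pressure and the QZc product".

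The pressure in that difference comes from a tonometer used to "record carotid pressure waveforms, which will be calibrated using brachial artery pressures", so it is in absolute mm Hg. No section says that diastolic or foot pressure is removed before QZc is subtracted. For details the section points to custom software and earlier publications; the authors "have published a tutorial detailing our analysis methods".

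Section 8.6 also plans the real part of the reflection coefficient in the first three harmonics. The synopsis lists the secondary endpoints in this domain as augmentation index, late systolic wall stress and aortic input impedance. The integral is not in that list.

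**The concern.** QZc is flow times a constant, so it is zero at the start of ejection. Measured pressure at that moment is diastolic pressure. The written difference therefore starts at diastolic pressure before any reflected wave has arrived, and that constant is carried through the whole integral. The section describes the result as net pressure due to reflections, and the formula does not deliver that.

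This matters because Aim 3 asks whether KNO₃ lowers late systolic load from wave reflections, and the drug may lower blood pressure. Section 11.2.1 reports that in the pharmacokinetics study "we found a mild (~12 mm Hg) asymptomatic reduction in blood pressure recorded at the time of our study visits". It also cites a meta-analysis with an "approximate 4 mm Hg reduction in systolic blood pressure and 1 mm Hg" diastolic reduction. Tonometry in the trial is done at the 6-week visit after the morning dose (Sections 5.3 and 5.5), so a visit pressure sets the calibration. If the formula is used literally, a plain fall in pressure lowers the measure and could be mistaken for a change in reflections. Section 10.2 names no adjustment for blood pressure.

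**Working it through.** The plan gives no mean, SD or power for this integral, so there is no stated figure to reproduce. Section 10.1 gives a detectable change of 4.2% in reflection magnitude, which is a different quantity.

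**1. Algebra.** Let P be measured pressure, D diastolic (foot) pressure and ET ejection time. Over ejection,

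∫(P − QZc) dt = D × ET + ∫[(P − D) − QZc] dt.

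The second term is the part that can represent reflections. The first is an offset. If there were no reflection at all, P would equal D + QZc and the written measure would still equal D × ET. With assumed D of 70–80 mm Hg and ET of 0.28–0.34 s, that is 70 × 0.28 = 19.6 to 80 × 0.34 = 27.2 mm Hg·s.

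**2. Effect of a uniform fall of c mm Hg** (pulse shape, flow, Zc and ET unchanged): the written measure changes by −c × ET and the foot-referenced measure by 0.

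| Fall c | Source of c | × 0.28 s | × 0.34 s |
|---|---|---|---|
| 1 mm Hg | meta-analysis, diastolic | −0.28 | −0.34 |
| 12 mm Hg | visit fall, only if uniform | −3.36 | −4.08 |

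Units are mm Hg·s. The ejection times are assumptions, since the documents give none.

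**3. Share of the measure.** Synthetic ejection waves were integrated at assumed pressures of 130/70, 145/75 and 150/65 mm Hg, ET of 0.28, 0.30 and 0.33 s, peak flow of 400 mL/s and Zc of 0.08 mm Hg·s/mL. The written integral was 25.4–33.8 mm Hg·s, and D × ET made up 64–77% of it.

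One case in full, 130/70 with ET 0.30 s:
- Offset: 70 × 0.30 = 21.0. Part above the foot: 6.3. Written measure: 27.3. Offset share: 21.0/27.3 = 77%.
- Uniform 12 mm Hg fall: 58 × 0.30 + 6.3 = 23.7. The change is −3.6, or −13.2%. The foot-referenced value stays at 6.3.

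Across all nine waves a uniform 12 mm Hg fall gave −11.7% to −13.2%.

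**4. A non-uniform fall.** For 4 mm Hg systolic and 1 mm Hg diastolic, with flow and Zc held fixed, the written measure fell by 0.81–0.99 mm Hg·s and the foot-referenced one by 0.53–0.66. The difference is 1 × ET = 0.28–0.33, about one third of the change. The rest comes from the lower pulse pressure, which foot-referencing does not remove.

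**5. Planned measures that ignore an offset.** A constant added to pressure sits at harmonic zero, so it does not reach the reflection coefficient in harmonics one to three. Augmentation index is formed from pulsatile pressure and is likewise unchanged by a uniform shift.

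**The case against.** The strongest reply is that the plan leaves the reference level unstated and does not positively specify total pressure. Section 8.6 calls the quantity net pressure from reflections, and the laboratory uses existing software and published methods that may already subtract foot pressure. This stands in part: the documents cannot show that the step is omitted. But the protocol does give a formula, and that formula does not produce what its own sentence describes.

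A reader might go further and infer that Aim 3 would be declared positive on a blood pressure fall alone. The documents do not support that:
- The integral is not among the synopsis secondary endpoints, and Section 10.2 calls the secondary aims exploratory.
- The reflection coefficient and augmentation index are already planned, and a pure offset would show up as disagreement with them.
- A fall in pressure is not established. Section 11.2.1 does not say which pressure fell by about 12 mm Hg and reports no ambulatory fall. The single-dose pilot in Section 3.5 saw changes of 0.17 mm Hg in mean and 0.7 mm Hg in systolic pressure (both P>0.85). In the meta-analysis pattern only the 1 mm Hg diastolic part acts as an offset.

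A reader might also infer that foot-referencing makes the measure independent of pressure. It does not, as step 4 shows, and the integral still scales with ejection time.

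**Conclusion.** Wrong as written, low severity. The presence of a diastolic pressure × ejection time term follows from the stated formula by algebra and needs no assumption about the patients. Its size does: about 0.3 mm Hg·s for a 1 mm Hg diastolic fall, and 3.4–4.1 mm Hg·s if a 12 mm Hg fall were uniform, both at an assumed ejection time of 0.28–0.34 s. The 64–77% share rests on synthetic waves. Whether the laboratory's software has the defect is unknown. The point bears on the mechanistic reading of Aim 3 and leaves peak VO₂ and total work untouched.

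**What to change.** In Section 8.6, define the measure as the integral over ejection of (measured pressure − diastolic foot pressure − QZc). Add that it is interpreted beside the augmentation index and the real part of the reflection coefficient, both already planned. State in the same place that changes in pulse pressure and ejection time can still move it.

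The cost is a sentence or two of text and, if the software does not already do this, one line of code. Waveforms are stored for off-line analysis (Section 5.1), so no new data are needed. If the software already references pressure to its foot, the text simply records existing practice. The downside is that values may not be comparable with any earlier analysis that did not subtract foot pressure.

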8.8 Cognitive Assessment

Computerized cognitive assessment testing will be performed using cogstate software (Cogstate; New Haven, CT). These tests will be administered to subjects prior to randomization and at the end of each intervention phase (6-week time point in both phases). The assessment includes a customized battery of seven tests that measure various cognitive domains. The battery includes the following tests:

EST NAME AND COGNITIVE DOMAIN PRIMARY OUTC		PRIMARY OUTCOME	INTERPRETATION		
International Shopping List Test Tell me the items on the shopping list.	Verbal learning	Number of correct responses remembering the word list on three consecutive trialsHigher score performance			
Gorton Maze Learning Test Find the hidden pathway.	Executive function	Number of errors learning the same hidden pathway across the consecutive learning trials	Lower score = Better performance		
Detection Test Has the card turned over?	Psychomotor function	Speed of performance; mean of the log ₁₀ transformed reaction times for correct responses	Lower score = Better performance		
Identification Test Is the card red?	Attention	Speed of performance; transformed reaction times for correct responses	Lower score = Better performance		
One Card Learning Test Have you seen this card before in this test?	Visual learning	Accuracy of performance	Higher score = Better performance		
One Back Test Is the card the same as the previous card?	Working memory	Speed of performance; transformed reaction times for correct responses	Lower score = Better performance		
International Shopping List Test - Delayed Recall Tell me the items on the shopping list that you learned earlier.	Memory	Number of correct responses	Higher score = Better performance		

8.9. Other assessments

Weight and Height: Weight will be measured to the nearest 0.1 kg with the use of calibrated scales, while the subjects are wearing light clothing and no shoes. Height will be measured at baseline to the nearest 0.1 cm using a wall-mounted stadiometer.

Physical Activity: We will measure activity level in all subjects with the Actigraph device, which has been previously validated. This device can be worn on the wrist, and measures acceleration each minute in the anterior-posterior, mediolateral, and vertical axis, and summarizes that information as a vector magnitude. The software will use this data to calculate physical activity in METS and steps. The accelerometer will be provided during both phase 1 and phase 2. We will give the devices (Aurora [see below] and Actigraph) to the subjects during approximately the final week of each interventional phase. We will ask the subjects to put the devices on and will provide informational materials to assist with device placement. We will also discuss device placement with the subjects at the study visits as well as over the phone as needed. Subjects will bring the devices to the endpoint assessment visits. Subjects will be fully oriented in the use of this device. The device may be removed for showering or swimming but otherwise should be worn continuously. The specific details in the use of this device will be provided to study subjects. We will use the average METS of activity over this time period as an estimate of physical activity. We will also records steps taken.

Ambulatory Pulse Wave Analysis: Ambulatory pulse wave analysis will be performed, when feasible, with a novel watch research device (Microsoft Aurora device). This device is not commercially available or FDA approved and is investigational. It continuously measures the radial pulse via a watch-mounted tonometer. The device also measures transit time from the heart to the wrist in an ambulatory fashion. The device will be worn outside of the exercise lab, as well as during the exercise studies themselves. The specific details in the use of this device will be provided to study subjects.

Genetic Expression Analysis: Blood RNA samples will be collected using BD PAXgene blood RNA tubes (BD Biosciences) in order to explore changes in genetic expression in response to the study medication (potassium nitrate) and whether patterns of genetic expression predict response to the study medication. Two 2.5 mL samples (total of 5 mL of blood) will be collected at each 6-week endpoint assessment visit.

Myocardial Perfusion Reserve: Subjects who agree to participate in the cardiac MRI sub-study will undergo a Stress Cardiac MRI during the last 2 weeks of each cross-over treatment phase. Study parameters assessed during this MRI scan will include: assessment of myocardial perfusion, assessment of myocardial fibrosis, and myocardial strain.

Myocardial perfusion: Stress perfusion images will be obtained following IV injection of regadenoson. Three to four short-axis perfusion images will be acquired each heart beat during the injection of the gadolinium-based contrast agent at a rate of 3 to 4 mL/s via a power injector during first pass of the contrast agent. Forty to sixty image frames will be obtained. Following reversal of regadenoson with intravenous aminophylline, cine images and delayed enhancement images (for focal fibrosis) will be obtained. At the end of the study, perfusion images will be obtained at rest using the same imaging protocol. Myocardial perfusion will be assessed from the time-intensity curves of the myocardium and blood pool. Overall MPR will be obtained as the ratio

of myocardial perfusion after vasodilator administration divided by the myocardial perfusion after reversal of the vasodilator ("rest" images).

Myocardial fibrosis: We will use cardiac MRI to assess diffuse myocardial fibrosis by computing the extracellular volume fraction from pre- and post-gadolinium normalized myocardial 1/T1 and blood 1/T1 changes, after correction for hematocrit. T1 mapping pre- and post- administration of a macrocycic gadolinium-based contrast agent (i.e., Gadobutrol 0.1 mmol/kg or an equivalent dose of Dotarem) will be performed using a modified Look-Locker inversion recovery (MOLLI) sequence with image analysis using CMR42 software (Circle CVI, Calgary, AB, Canada).

Myocardial strain: We will assess myocardial longitudinal and circumferential strain using Cine Displacement ENcoding with Stimulated Echoes (DENSE) sequences.

9. MULTICENTER MANAGEMENT PLAN

9.1. Study Chair/Grant Principal Investigator

[name] will serve as the Study Chair and grant Principal Investigator for this protocol. In this role, he will administer the grant, and communicate with the NIH about study progress. He will communicate with site PIs regarding the science and any operational issues that arise during the trial, establish subcommittees and working groups to complete specific activities, monitor study implementation across sites (Penn, Northwestern, and Corporal Michael J. Crescenz VAMC), and hold regular investigator calls/meetings. As DSMB coordinator, he will convene an independent DSMB, communicate with the DSMB, and participate in open DSMB meetings. [name] will supervise the investigative team to develop and coordinate procedures and generate reports and presentations. He will maintain communication with the DSMB and will provide central fiscal management and reporting. Other roles of [name] will include directing the echocardiography and arterial hemodynamics core laboratory for this trial.

